8.7.2.2 Sensitivity Analyses for IGA

The first sensitivity analysis for the dichotomized IGA success will use a repeated measures logistic regression model (generalized estimating equations), with dichotomized IGA success as the dependent variable and treatment, analysis center, visit (i.e., Weeks 2, 4 and 8), and treatment group by visit interaction as independent factors. In this analysis, data from all post-baseline visits will be included with no imputation for missing data.

The second sensitivity analysis will use the model based multiple imputation method to impute missing data for the dichotomized IGA data. The multiple imputation will involve 3 principal tasks:

1. Missing values will be filled in 5 times to generate 5 complete data sets. The imputation model used logistic regression with factors of treatment group and analysis center (i.e., the imputation model will be the same as the analysis model).

Syntax:

```
proc mi data=datain out=dataout seed=&seed. nimpute=5 <options>;  
  class trtpn sitegr1 diiga;  
  var trtpn sitegr1 diiga;  
  monotone logistic (sitegr1=trtpn);  
  monotone logistic (diiga=trtpn sitegr1);  
run;
```

2. Each complete data set will be analyzed with a logistic regression a factors of treatment group and analysis center.
3. Results from these analyses will be combined into a single inference.

One random seed will be needed to impute IGA. The following random seed has been pre-specified by using a random number generator:

IGA Seed= 65762814

8.7.3 Secondary Efficacy Analysis

Appropriate descriptive statistics will be computed for all secondary efficacy parameters.

The percent change from Baseline to Week 12 in inflammatory lesion counts and the absolute change from Baseline in inflammatory lesion counts at Week 8 and Week 4 will be analyzed using the same ANCOVA method described for the primary endpoint.

The proportion of subjects who are dichotomized to success (“clear” or “almost clear”) at Week 8 and Week 4 will be analyzed using the same logistic analysis method described for the co-primary endpoint.

A stepwise process will be conducted for testing the secondary efficacy endpoints in order to control for multiplicity, refer to Section 8.1.8.

The secondary efficacy analysis will be presented on only the ITT population.

8.7.4 Supportive Efficacy Analysis

Appropriate descriptive statistics will be computed for all supportive efficacy parameters.

In addition, the mean change comparison in PAPSS item 1 (burning), item 2 (itching), item 3 (redness) and item 4 (bumps) from Baseline to Week 12 will be analyzed using an analysis of variance (ANOVA) with factors of treatment, analysis center, and the respective Baseline score. Missing values will not be imputed.

A set of cumulative distribution function curves will be generated to allow for the evaluation of within-person change by treatment group. Specifically, 5 plots will be generated showing the change from Baseline to Week 12 (and/or other, earlier time points if so desired) by the cumulative percent of subjects for each of the treatment arms (change on the x-axis will be expressed as absolute change) on:

- PAPSS total scale scores

- The total scale score is the sum of PAPSS items 1 through 4.
 - PAPSS item 1 (burning) scores
 - PAPSS item 2 (itching) scores
 - PAPSS item 3 (redness) scores
 - PAPSS item 4 (bumps) scores

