14.5. Patient Reported Outcomes (PRO)

There are six PRO questionnaires to be administered in the study and each is summarized below. Each will be administered to all patients during the designated study visits with instruction from the Study Staff that they be completed:

- Only by the patient without amendment or interpretation of the patient's response by a clinician or anyone else.
- Prior to any other assessments or procedures.

In the event the patient skips any questionnaire items; the Study Staff will ask the patient to complete the form. The PRO questionnaire data will be entered into EDC, and a copy will be placed with the patient source at the site according to the ICH-GCP guideline (4.9.5).

The PAPSS ([Appendix 2](#)): The PAPSS is a 4-item questionnaire that asks patients to assess the severity of their rosacea symptoms (burning, itching, redness, and bumps) in the 24 hours prior to assessment on an 11-point numeric rating scale (NRS) ranging from “0=none” to “10=worst possible symptom”. The questionnaire can be completed in less than one minute and is administered via pen-and-paper at the Baseline visit and site visits at Weeks 2, 4, 8 and 12 (End of Study) or early termination. Items can be scored individually as well as together to form a total score. In the present context, within visit scores from Items 1 (burning), 2 (itching), and 4 (bumps) are summed and averaged to create a total score that will be used to evaluate efficacy hypotheses.

The PAPI ([Appendix 3](#)): The PAPI is a 3-item questionnaire that asks patients to assess the papulopustular rosacea related embarrassment, self-consciousness, and frustration in the 7 days prior to assessment on an 11-point NRS ranging from 0 [“not (concept) at all”] to 10 [“extremely (concept)”]. The questionnaire can be completed in less than one minute and is administered via pen-and-paper at the Baseline visit and site visits at Weeks 2, 4, 8 and 12 (End of Study) or early termination. Items can be scored individually as well as together to form a total score.

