2. PREFACE

This Statistical Analysis Plan (SAP) describes the statistical analyses as it is foreseen before breaking the blind. The SAP will serve as a compliment to the study protocol and supersedes it in case of differences. In case of major differences between the study protocol and SAP, e.g. changes in the analysis related to the primary endpoint, a protocol amendment will be considered. The SAP may be updated during the study conduct and will be finalized before breaking the blind.

The following documents were reviewed in preparation of this SAP:

- Clinical Study Protocol SGT-54-02
 - Version 1.0 issued on 15MAR2018,
 - Version 2.0 issued on 30APR2018,
 - Version 3.0 issued on 07JUN2018,
 - Version 4.0 issued on 13NOV2018
- Case report form (CRF) for SGT-54-02.
- ICH E9 Guidance on Statistical Principles for Clinical Trials.
- ICH E3 Structure and Content of Clinical Study Reports (CSRs)

The reader of this SAP is encouraged to also read the clinical protocol for details on the conduct of this study, and the operational aspects of clinical assessments and timing for completing a patient in this study.

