8.1.8 Multiple Comparisons/Multiplicity

In testing the secondary efficacy endpoints the overall Type I error will be controlled by requiring the two co-primary efficacy endpoints to be statistically significant. Specifically, failure of either one of the primary efficacy endpoints will invalidate the statistical significance of the secondary efficacy endpoints.

A stepwise process will be conducted for testing the secondary efficacy endpoints in order to control for multiplicity. These tests will be performed for only the ITT population. The testing process will terminate whenever a statistical test for a step is not significant. All subsequent tests for the remaining steps will be considered not significant. The order of testing is provided below.

Step Number	Secondary Endpoint
1	Percent change in inflammatory lesion count from Baseline to Week 12
2	Absolute change in inflammatory lesion count from Baseline to Week 8
3	Proportion of patients with the primary measure of success “Clear” (0) or “Almost clear” (1) in the IGA relative to Baseline at Week 8
4	Absolute change in inflammatory lesion count from Baseline to Week 4
5	Proportion of patients with the primary measure of success “Clear” (0) or “Almost clear” (1) in the IGA relative to Baseline at Week 4

In testing the supportive efficacy endpoints, the overall Type I error will be controlled by the Benjamini-Hochberg method. The Hochberg and Benjamini adaptive step-down Bonferroni method will be used within PROC MULTTEST in SAS (AHOLM option in PROC MULTTEST).

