10. CHANGES IN THE PLANNED ANALYSES

There are no changes in the conduct of the study, but there are minor changes to the planned analyses.

Due to feedback received, the primary efficacy analysis was adjusted back to the original analysis. The modification to only use the non-parametric version as described in v4 of the protocol was not accepted by the agency. The original approach uses an ANCOVA analysis with the terms for treatment, analysis center, and Baseline count (and treatment-by-center interaction if the term is significant at 0.10). If the two-sided p-value for the skewness test is significant at 0.01, then the rank-transformed data will be used instead of nominal values. The original approach was accepted by the agency.

The pooling analysis described in the protocol is updated in the statistical analysis plan (SAP) to reflect the intended analysis. The protocol discusses pooling sites with five or fewer subjects enrolled in each treatment arm. Taking into consideration the randomization ratio, the SAP requires ten subjects in the active treatment arm and five subjects in the vehicle group.

As part of the pooling analysis, the treatment effect within investigational site must be investigated. The protocol states the site main effect will be examined by using a one-way analysis of variance (for lesion count variables) or a logistic regression analysis (for dichotomized IGA) with a factor of site. The SAP instead explains site will be incorporated into the primary analysis models. Change from Baseline in lesion counts will be analyzed with an ANCOVA (unranked or ranked) with factors of treatment group, investigational site and treatment group by investigational site interaction, and the respective Baseline lesion count variable as a covariate. The dichotomized primary endpoint will be analyzed with a logistic regression with factors of treatment group, investigational site and the interaction term of treatment group by investigational site.

The protocol describes repeated measures sensitivity analyses for the primary efficacy endpoints. Treatment group, analysis center and visit are listed as factors for the repeated measures analyses. In addition to these factors, the SAP includes a factor of treatment group by visit interaction.

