^a Least squares means, standard deviations and treatment p-value from an analysis of covariance with factors of treatment and analysis center and the Baseline lesion count as a covariate. Negative least squares means values represent decrease from Baseline.

^b Skewness test, based on methods presented by J.H. Zar (1984), assessed for each imputed dataset. The average p-value is presented.

^c P-value from a ranked analysis of covariance with factors of treatment and analysis center and the Baseline lesion count as a covariate.

^d P-value from a logistic regression with factors of treatment group and analysis center.

Note: Multiple imputation (MCMC) used to impute missing values.

SOURCE: USERNAME\SPONSOR\PROJECT\JOBNAME (DATE, TIME)

Table 14.2.6.1: Secondary Efficacy Analyses
(Intent-to-Treat Population)
(Page 3 of 3)

	E-BPO 5% Cream (N=xxx)	Vehicle Cream (N=xxx)	Skewness P-Value	Treatment P-Value
Inflammatory Lesion Count – Absolute Change from Baseline to Week 4				
LSMean ^a	xx.x	xx.x	x.xxx ^b	x.xxx ^a
LSSD ^a	xx.xx	xx.xx		x.xxx ^c
Achieving Clear or Almost Clear at Week 4				
Success	xx.x%	xx.x%	N/A	x.xxx ^d
Failure	xx.x%	xx.x%		

^a Least squares means, standard deviations and treatment p-value from an analysis of covariance with factors of treatment and analysis center and the Baseline lesion count as a covariate. Negative least squares means values represent decrease from Baseline.

^b Skewness test, based on methods presented by J.H. Zar (1984), assessed for each imputed dataset. The average p-value is presented.

^c P-value from a ranked analysis of covariance with factors of treatment and analysis center and the Baseline lesion count as a covariate.

^d P-value from a logistic regression with factors of treatment group and analysis center.

Note: Multiple imputation (MCMC) used to impute missing values.

SOURCE: USERNAME\SPONSOR\PROJECT\JOBNAME (DATE, TIME)

Table 14.2.7.1: Patient Assessment of Papulopustular rosacea Signs and Symptoms (PAPSS) Analyses at Week 12 (Intent-to-Treat Population)

	E-BPO 5% Cream (N=xxx)	Vehicle Cream (N=xxx)	Treatment P-Value
PAPSS Total Scale Score – Absolute Change from Baseline to Week 12			
LSMean ^a	xx.x	xx.x	x.xxx ^a
LSSD ^a	xx.xx	xx.xx	
PAPSS Burning – Absolute Change from Baseline to Week 12			
LSMean ^a	xx.x	xx.x	x.xxx ^a
LSSD ^a	xx.xx	xx.xx	
PAPSS Itching – Absolute Change from Baseline to Week 12			
LSMean ^a	xx.x	xx.x	x.xxx ^a
LSSD ^a	xx.xx	xx.xx	

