PAPSS Redness – Absolute Change from Baseline to Week 12			
LSMean ^a	xx.x	xx.x	x.xxx ^a
LSSD ^a	xx.xx	xx.xx	
PAPSS Bumps – Absolute Change from Baseline to Week 12			
LSMean ^a	xx.x	xx.x	x.xxx ^a
LSSD ^a	xx.xx	xx.xx	

^a Least squares means, standard deviations and treatment p-value from an analysis of variance with factors of treatment, analysis center, and the respective Baseline score. Negative least squares means values represent decrease from Baseline.

Note: No imputation of missing values. To control family-wise type I error rate at 5%, the Benjamini-Hochberg procedure (Hochberg and Bejamini adaptive step-down Bonferroni method) was utilized, and each p-value with an (*) is to be considered statistically significant.

SOURCE: USERNAME\SPONSOR\PROJECT\JOBNAME (DATE, TIME)

Table 14.2.8.1: Summary of Patient Assessment of Papulopustular Rosacea Signs and Symptoms (PAPSS) at Each Evaluation
(Intent-to-Treat Population)
(Page 1 of 15)

Total Scale Scores	E-BPO 5% Cream (N=xxx)	Vehicle Cream (N=xxx)
Baseline		
n	xx	xx
Mean	xx.x	xx.x
SD	xx.xx	xx.xx
Median	xx.x	xx.x
Min. to Max.	xx to xx	xx to xx
Week 2		
n	xx	xx
Mean	xx.x	xx.x
SD	xx.xx	xx.xx
Median	xx.x	xx.x
Min. to Max.	xx to xx	xx to xx
Change from Baseline		
n	xx	xx
Mean	xx.x	xx.x
SD	xx.xx	xx.xx
Median	xx.x	xx.x
Min. to Max.	xx to xx	xx to xx

Note: No imputation of missing values.

Total scale score is the sum of all PAPSS items.

SOURCE: USERNAME/SPONSOR/PROJECT/JOBNAME (DATE,TIME)

Table 14.2.8.1: Summary of Patient Assessment of Papulopustular Rosacea Signs and Symptoms (PAPSS) at Each Evaluation
(Intent-to-Treat Population)
(Page 2 of 15)

Total Scale Scores	E-BPO 5% Cream (N=xxx)	Vehicle Cream (N=xxx)
Week 4		
n	xx	xx
Mean	xx.x	xx.x
SD	xx.xx	xx.xx
Median	xx.x	xx.x
Min. to Max.	xx to xx	xx to xx
Change from Baseline		
n	xx	xx
Mean	xx.x	xx.x
SD	xx.xx	xx.xx
Median	xx.x	xx.x
Min. to Max.	xx to xx	xx to xx
Week 8		
n	xx	xx
Mean	xx.x	xx.x
SD	xx.xx	xx.xx
Median	xx.x	xx.x
Min. to Max.	xx to xx	xx to xx
Change from Baseline		
n	xx	xx
Mean	xx.x	xx.x
SD	xx.xx	xx.xx
Median	xx.x	xx.x
Min. to Max.	xx to xx	xx to xx

Note: No imputation of missing values.

Total scale score is the sum of all PAPSS items.

SOURCE: USERNAME\SPONSOR\PROJECT\JOBNAME (DATE,TIME)

Table 14.2.8.1: Summary of Patient Assessment of Papulopustular Rosacea Signs and Symptoms (PAPSS) at Each Evaluation
(Intent-to-Treat Population)
(Page 3 of 15)

Total Scale Scores	E-BPO 5% Cream (N=xxx)	Vehicle Cream (N=xxx)
Week 12		
n	xx	xx

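### The SAP's PAPSS total adds the redness item that the protocol's efficacy total leaves out, without declaring it, and the PAPSS multiplicity note claims 5% family-wise control for Benjamini-Hochberg over an unstated family of four or five tests

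*SAP*

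**What the plan says.** **Score.** Protocol 14.5 describes four PAPSS items, each rated 0 to 10, and says that "within visit scores from Items 1 (burning), 2 (itching), and 4 (bumps) are summed and averaged to create a total score", to be used for efficacy hypotheses. Redness (item 3) is not in that total. SAP 8.7.4 says "The total scale score is the sum of PAPSS items 1 through 4", and the notes to the Table 14.2.8.1 shell repeat it: "Total scale score is the sum of all PAPSS items".

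**Precedence and disclosure.** SAP section 2 says "The SAP will serve as a compliment to the study protocol and supersedes it in case of differences". Section 10 opens with "There are no changes in the conduct of the study, but there are minor changes to the planned analyses". It then covers the primary analysis, pooling, the site effect, the repeated-measures models, imputation and seeds, and geographic region. PAPSS scoring is not mentioned.

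**Multiplicity.** Protocol 19.4.4 names Benjamini-Hochberg for the four PAPSS item tests at Week 12. SAP 8.1.8 says "In testing the supportive efficacy endpoints, the overall Type I error will be controlled by the Benjamini-Hochberg method" and in the next sentence instructs the adaptive step-down Bonferroni method through the AHOLM option of PROC MULTTEST. The note to Table 14.2.7.1 gives both names to one procedure and says that it holds the family-wise error at 5%.

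**Family.** Protocol 19.4.4 and SAP 8.7.4 each list four tests, one per item. Table 14.2.7.1 has a further row, "PAPSS Total Scale Score", with its own treatment p-value under the same starring note. SAP 8.1.8 does not list the members of the family.

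**The concern.** Adding redness changes what the total measures; going from a mean to a sum only rescales it. The summaries of the total, its p-value in Table 14.2.7.1 and its cumulative distribution plot would all describe a different construct from the protocol's score. A reader relying on section 10 would not learn of it. The result could move either way, depending on how redness responds.

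The multiplicity text has a separate fault. If the programmer follows the name, the 5% family-wise statement is not true in general. If the programmer follows the SAS option, the label is wrong. A reader of the finished table could not tell which procedure produced the asterisks, or whether the total's p-value counted in the adjustment.

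**Working it through.** **1. The two totals.** Take changes in the order burning, itching, redness, bumps.

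| Change | Protocol: mean of items 1, 2, 4 | SAP: sum of items 1-4 |
|---|---|---|
| (0, 0, -4, 0) | (0+0+0)/3 = 0 | -4 |
| (-1, -1, 0, -1) | -3/3 = -1.0 | -3, or -0.75 per item |

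The protocol score runs 0-10 and the SAP score 0-40. Redness carries 0% of the first and 1/4 = 25% of the second.

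**2. Effect on sensitivity.** The documents give no item SDs or correlations. Assume equal SDs, a common inter-item correlation r, equal effects on items 1, 2 and 4, and a redness effect k times theirs. The variance of a sum of three items is proportional to 3+6r, and of four items to 4+12r. The ratio of standardised effects, SAP total to protocol total, is then

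[(3+k)/3] × sqrt[(3+6r)/(4+12r)]

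| | r = 0.3 | r = 0.5 | r = 0.7 |
|---|---|---|---|
| k = 0 (redness does not respond) | 0.795 | 0.775 | 0.762 |
| k = 1 (responds equally) | 1.060 | 1.033 | 1.016 |
| k = 2 (responds twice as strongly) | 1.325 | 1.291 | 1.270 |

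For k = 0 and r = 0.3: 1 × sqrt(4.8/7.6) = 0.795.

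**3. The 5% family-wise figure.** Take four independent tests, two of them true nulls and the other two with p-values near zero. Benjamini-Hochberg then rejects a true null if the smaller null p-value is at most 0.05 × 3/4 = 0.0375, or if both are at most 0.05:

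1 - (1 - 0.0375)² + 0.0125² = 0.0737

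So the stated 5% is not reproduced for Benjamini-Hochberg. Simulated two-sided tests at 0.05 gave these family-wise rates:

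| Setting | Benjamini-Hochberg | AHOLM | Holm |
|---|---|---|---|
| Independent tests, very large effects: maximum | 7.4% (4 tests), 8.8% (5 tests) | 5.5% | about 5% |
| r 0.3-0.7, one to three items shifted 2 or 3 SE, 4 tests | 2.95-6.28% | 2.60-5.27% | 2.19-4.39% |
| Same, 5 tests | 2.84-5.88% | 2.47-5.02% | 2.07-3.69% |

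In the last two rows the fifth test is the standardised sum of the four items. AHOLM compares the i-th smallest of m p-values with 0.05/min(estimated true nulls, m-i+1). SAP 8.1.8 does not state the estimator, so a lowest-slope estimate was assumed; the AHOLM column is for that estimate rounded down. With all nulls true and r 0.3-0.7, AHOLM gave 5.5-6.1% with the estimate rounded down and 4.5-5.0% rounded up.

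**4. Family size.** Suppose the item p-values are 0.012, 0.2, 0.3 and 0.4. With four tests the smallest is compared with 0.05/4 = 0.0125 under both Benjamini-Hochberg and Holm, so one item is starred. Add a total with p = 0.2 and the threshold becomes 0.05/5 = 0.010, so none is starred. AHOLM, with the assumed estimator, still stars that item in the family of five. The two procedures that the note equates therefore disagree on the same p-values.

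**The case against.** **The scoring change reaches little.** The protocol plans no test of the total: 19.4.4 tests the four items, and the total appears only among the cumulative distribution plots. The SAP states its definition openly in 8.7.4 and in the table notes, and redness keeps its own analysis. This is right about reach, and no information is lost. But Protocol 14.5 does assign its score to efficacy hypotheses, the SAP shell gives the total a p-value, and section 10 records changes as small as seed counts while omitting this one.

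**The multiplicity fault is mostly a name.** AHOLM is the only executable instruction, and it stays near 5%. This stands as to size: the 7.4% and 8.8% figures belong to a procedure the SAP names but does not code, and only in an extreme setting. It does not rescue the note, which attaches a family-wise guarantee to Benjamini-Hochberg.

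**The text names four tests.** True; the fifth p-value is only in the shell. But the shell places it under the starring note, and nothing says that it is outside the family.

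**The AHOLM figures depend on the assumed estimator.** They do, and the effect of rounding is shown above. The conclusion does not rest on them.

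**Moving to Holm replaces a method when the defect is wording.** Fair. Keeping AHOLM under its own name would also cure the fault.

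**Conclusion.** The concern holds and should be corrected before unblinding. Three facts rest on the text alone: the SAP total includes redness and the protocol's does not, with no entry in section 10; two different procedures are presented as one with 5% family-wise control; and the table prints five p-values where the text names four tests.

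The sizes rest on assumptions. With equal item SDs and correlations of 0.3-0.7, the SAP total's standardised effect is 0.76 to 1.33 times the protocol score's, depending on redness, so no direction of bias is claimed. Benjamini-Hochberg's excess over 5% is modest in plausible settings (up to 6.3%) and disappears in many. Only supportive results are touched. The co-primary tests, the five-step secondary sequence and the sample size are unaffected.

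**What to change.** All changes are to the SAP; no protocol amendment is needed.

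1. In 8.7.4, Tables 14.2.7.1 and 14.2.8.1 and Figure 14.2.3.1, compute the total as the mean of items 1, 2 and 4. Otherwise keep the four-item sum, and declare and justify it in section 10.
2. In 8.1.8, list the family: either the four items, with the total descriptive and unstarred, or five tests including the total.
3. In 8.1.8 and the Table 14.2.7.1 note, name one procedure and the error rate it controls: Holm for 5% family-wise control, or Benjamini-Hochberg labelled as false discovery rate control. AHOLM alone is also acceptable if the Benjamini-Hochberg label is removed and its family-wise control is described as approximate. List any departure from Protocol 19.4.4 in section 10.

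The cost is one derivation line and some wording. Holm may star slightly fewer items. If all four respond by 2-3 SE with r 0.3-0.7, the expected number starred is 1.47-3.15 of 4 with Holm, 1.63-3.21 with AHOLM (estimate rounded down) and 1.70-3.30 with Benjamini-Hochberg. Matched by setting, Holm stars 0.06-0.19 fewer than AHOLM (from 3.214 - 3.150 to 1.677 - 1.490). Data collection does not change.
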